#### **6.3.4. Subject withdrawal criteria**

The subject is allowed to withdraw from the investigation at any time for whatever reason without any consequences for their future treatment outside the clinical investigation. Investigator may withdraw a subject from the investigation at any time if they judge it to be the subject's interest.

The investigator must withdraw a subject from the investigation due to:

- Non compliance with the CIP impacting the scientific integrity of the investigation
- If subject's safety and wellbeing is compromised by further participation.

Withdrawn subjects will not be replaced by new subjects.

A subject who is withdrawn from the investigation, for any reason, will be encouraged to contact the investigator if problems arise that the subject believes are related to the clinical investigation. Subjects who have not experienced any adverse events will not be followed up. For subjects who experience adverse events, see section 14.

#### **6.3.5. Point of enrolment**

A subject is considered enrolled in the investigation when the written informed consent is obtained. The expected duration for each subject is described in section 6.1.

#### **6.3.6. Total expected duration of the clinical investigation**

The dates below are approximate and no subjects will be enrolled before all required approvals have been obtained. Changes greater than  $\pm$  3 months will be notified to EC and regulatory authorities.

Activity	Estimated time
First subject enrolled	November 2018
Last subject enrolled	December 2018
Last subject completed (LSLV)	February, 12 th , 2019
Final Report	February 2020

#### **6.3.7. Total number of subjects**

Based on sample size calculations (see section 7.2) 21 one-piece users should be included in this investigation. However, to take potential drop-out into account a total of 25 one-piece users will be included (allocated a subject number).

### **6.4. Procedures**

#### **6.4.1. Clinical investigation-related procedures**

See section 6.4.4 Flow-chart for a more detailed overview of the clinical investigation-related procedures at visit and 6.4.5 for a more detailed overview

[REDACTED]

## Site visits

Before initiation of the clinical investigation, sponsor must be provided with key personnel's signed and dated curriculum vitae (not more than two years old) to verify their qualifications. Key site personnel are those, who conduct the clinical investigation and obtain subject data. Also, the sponsor will ensure that all site personnel are trained in the investigation procedures, how to complete the CRFs, procedure for reporting an adverse event and serious adverse event (how, when, to whom), and who to contact in case of emergency related to the investigational device.

### Visit 0 (Information and Inclusion visit)

If a potential subject is interested in participating after the first contact, a visit (visit 0) will be arranged in a room reserved to ensure privacy and quiet surroundings at the investigators clinic/department. When arranging the visit, it will be ensured, that the subject has received the Subject Information Form prior to the visit. The subjects will receive both written and verbal information to ensure that the subject understand what was read and explained and can freely agree to participate in the investigation. The subject will, beforehand, also be informed about the possibility of bringing a companion to the informational visit and to any possible subsequent visits. During the visit the Investigator or delegated personnel will provide oral information about the investigation based on the Subject Information Form. The subjects have the right to wait 24h before deciding on participation. The information visit and the Visit 0 can be the same day.

If/when subjects decide to participate they will be asked to sign the Informed Consent Signature Form and other relevant forms (see section 13). If a subject so desires, and it is certain that it is understood what the investigation entails and the relevant forms have been signed the subjects are considered enrolled in the investigation. Enrolled subjects that fulfils the in- and exclusion criteria are allocated a subject number, and hereafter demographics, baseline data and concomitant medications is recorded by Investigator or delegated personnel.

Visit 0 and visit 1 can be combined.

### Test visits (V1, V2, V4, V5 and V6)

During test visit 1, the subject will be introduced to the clinical app on how to complete the questionnaires and take pictures. At visit 2 the test products will be handed out. At this visit the subjects will be trained according to the IFU, in preparation of the product (e.g. hole size), preparation of skin before application (e.g. cleaning and wiping), application of product (e.g. correct position and applying pressure to the baseplate), removal of product and storage of the product.

At each test visit objective skin measurement will be done, the product changed at the visit will be collected for further analysis, pictures of cut product will be taken, stoma condition, skin condition and safety endpoints will be registered. At test visit 2 and 6 questions regarding feeling of security, handling, leakage scale and quality of life will be completed by subject. An output sample will be collected for further analysis at test visit 1 and 2. The output samples and products changed at the visit will be stored in a separately CP300 allocated freezer at site, and send on an ongoing basis to Coloplast A/S, Humlebæk, Denmark. The samples of output will not be stored longer than it takes to collect and analyse the samples. The sample will be destroyed directly after analysis.

At test visit 6 questions about product preference will be completed by subject.

### Product change

At every product change the subjects will record reason for change, pain/discomfort, skin condition and use of accessories. Wear time of the product will be calculated from the time for product change registered in the app.

At every product change the subject will be asked to take a picture of the back side of the changed products (leakage), the peristomal skin and the cut product to be applied. [REDACTED]

Subjects will also be informed about the possibility to contact a Coloplast nurse during the investigation, to ensure questions and experiences addressed answered properly. This will be a secondary contact person in addition to the study nurse at site.

### **Safety follow-up**

To follow safety closely during the investigation, a safety visit (V3) is planned after one week of wearing the test product. The safety visit will, when logistically possible, be conducted by Sponsor at site, supported by Investigator or study nurse. The subjects will be asked about all experiences with their stoma during the investigation and other safety endpoints, following the safety interview guide (see Appendix 4). In addition, the product changed at the visit will be collected for further analysis.

To follow safety further, Sponsor might also wish to be presented at subjects' test visits. Sponsor will observe during the test visit and might ask the subject questions about experiences with their stoma during the investigation and other safety endpoints, following the safety interview guide (section 20.4).

### **Interview**

The subjects will be offered to participate in two interviews. The interviews will be about the subjects experience with the test product and might include a change of product. The subjects can participate in the investigation without being interviewed. The interviews, or relevant parts, might be video recorded, tape recorded or photos might be taken. The subjects will be asked for consent, but can participate in interviews without completing video, tape or photos.

- **Interview 1:** at test visit 6 (at site) or within 14 days after termination (at home). If the interview is part of the test visit, Sponsor will be present during the test visit. At first, they will ask the subject unprobed questions to get their immediate response to the product. Hereafter, the subject can continue the test visit as usual. At the end of the visit, the interviewer will interview the subject following the interview-guide. If the subject has consented to photo, video and/or tape recording the interviewer might do so during relevant parts of the interview and test visit.
- **Interview 2:** a follow-up visit at home within three months after last patient out.

The information needed from interviews are estimated to be covered by up to 6-10 subjects, but all will be asked if they would like to participate, if more than ten are needed. If fewer than six subjects agree to be interviewed, we will settle for the number that have agreed. This has been decided since the main endpoints are covered in the CRF. It is known from experience that it is not always possible to perform all the interviews face-to-face due to logistics. In order, not to lose important information about the tested products, interviews may be by telephone / video call, in cases the interviewers cannot be present at the visits.

In addition, the study nurses and/or investigator may be interviewed during and/or within three months after termination of the investigation.

All interviews will be performed by Sponsor following an interview guide (Appendix 5).

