#### 6.1.5. Discussion of clinical investigation design

The new test product is intended for people with an ileostomy and for colostomists with liquid output. The two groups experience the same issues regarding leakage and skin problems and could therefore benefit from the product.

SenSura® Mio and SenSura® users are chosen and will be considered as one group, since results from a previous investigation showed no difference between the two user groups regarding inner circle TEWL (primary endpoint).

The duration of Test Period 1 (14 (-2/+15) days) and two test visits in the period is found adequate to assess baseline data on the wear time, leakage pattern and skin condition of the subject. The test product is tested for 28 (-4/+12) days to ensure that the skin will have time to adjust to the new conditions, reach a steady state, and for the subjects to test an adequate number of products to give a thorough evaluation of the products.

To follow safety closely and ensure proper compliance and no unexpected events related to the test product, the first five subjects will be enrolled at the Coloplast Humlebæk Site DK001 (Sponsor). In addition, and due to Christmas holiday, follow-up logistics and planning purpose, the following subjects, at other sites than DK001, will be invited for the test visit 1 during week 49-51 (December 2018) and for their test visit 2 during week 1 and 2 (January 2019).

 CP275 – A clinical investigation evaluating three new 1-piece ostomy products

Danish Ethical Committee registration number H-17005054/Danish Competent Authorities registration number DMA-2017022387

In this investigation, a part of the information about the products is obtained via interviews (qualitative data). The interviews allow for detailed questions (in the form why, when, how) that can be adjusted individually per each subject's experience. This gives more details about the subject's experience with the test product. However, some drawbacks also occur with this method of obtaining information, as the interview data is subjective and cannot be quantified. The interviews may also cause a positive bias towards Coloplast. Thus, in this explorative investigation, the main endpoints are obtained by CRFs (from all subjects) and the interviews are used for supplementary information. The data collected by interviews will be handled confidentially, as all other data collected in this investigation.

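### When Interview 1 is held at V6, the sponsor asks about the test product before the V6 questionnaires, with no counterpart at V2: an avoidable asymmetry of unknown size and uncertain direction

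*Combined protocol and SAP*

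**What the plan says.** Section 6.4.1 (Interview) offers subjects a voluntary Interview 1 about their experience with the test product. It takes place either on site at V6 or at home within 14 days after termination. For the first option the plan states: "If the interview is part of the test visit, Sponsor will be present during the test visit". It then sets an order of events:

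1. "At first, they will ask the subject unprobed questions to get their immediate response to the product"
2. "Hereafter, the subject can continue the test visit as usual"
3. "At the end of the visit, the interviewer will interview the subject following the interview-guide"

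Section 6.4.1 (Test visits) describes what the ordinary visit contains: "At test visit 2 and 6 questions regarding feeling of security, handling, leakage scale and quality of life will be completed by subject". It adds: "At test visit 6 questions about product preference will be completed by subject".

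Section 6.1.5 acknowledges a risk: "The interviews may also cause a positive bias towards Coloplast". Its answer is that the main endpoints are taken from CRFs for all subjects, while the interviews only supplement them.

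**The concern.** The four questionnaires are completed once at the end of the comparator period (V2) and once at the end of the test period (V6). There is no randomisation (section 6.4.6) and no blinding (section 6.4.7), and every subject takes the products in the same order (section 6.1). The within-subject V6-V2 change is therefore the only product comparison these forms can give. Anything done to the subject just before the V6 forms but not before the V2 forms enters that change directly. Talking to the manufacturer's staff about one of the two products is such a step. Preference is asked only at V6, so for these subjects it follows a conversation about one product alone.

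Section 6.4.7 already accepts that subjective parameters may be biased because the products look different. This would be an additional influence, and one that the order of procedures could avoid.

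**Working it through.** The plan states no figure on this point. The check is of the order of procedures, followed by simple arithmetic on the share of subjects exposed.

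**Order at V6.** Section 6.4.1 (Interview) places the opening questions first, the usual visit second and the guided interview last. Section 6.4.1 (Test visits) puts the questionnaires within the usual visit. Nothing in the plan moves them ahead of the opening questions. Read together, the sponsor's questions come before the forms.

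**Order at V2.** No interview is scheduled. Section 6.4.1 (Safety follow-up) lets the sponsor attend any test visit, V2 included, and ask questions from the safety guide. The questions listed in section 20.4 concern general health, the stoma and the abdomen, not the response to a product. V2 can therefore involve sponsor contact, but it has no equivalent of the opening product questions.

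**Does the CRF argument in section 6.1.5 cover this?** Section 6.4.8 makes the subject questionnaire one of the three parts of the CRF, and that part holds security, handling, quality of life, leakage scale and preference. Keeping interview notes out of the CRF does not help if the CRF answers are given after the interview has begun.

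**Share exposed.** Let k be the number of subjects whose Interview 1 takes place at V6, n the number analysed, and d the mean shift in a V6 score among those k subjects. If the other subjects are unaffected, the overall mean V6-V2 change moves by (k/n) × d.

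- Inputs: 6-10 interviewees expected, fewer accepted, and all may be asked if more than ten are needed (section 6.4.1, Interview); 25 subjects included (section 6.3.7); 20% drop-out assumed (section 7.4).
- No Interview 1 at V6: 0/25 = 0, so no shift.
- Six, all at V6: 6/25 = 24%, shift 0.24d.
- Ten, all at V6: 10/25 = 40%, shift 0.40d.
- If 20% drop out, n = 25 × 0.80 = 20. If every interviewee is among those 20, the shares are 6/20 = 30% and 10/20 = 50%, so the shift is at most 0.50d.
- Every subject interviewed at V6: 100%, shift d. This is possible only if the sponsor goes well beyond ten.

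The documents give neither the size nor the sign of d, so the bias itself cannot be computed.

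**The case against.** A reader might infer three stronger things. The documents do not support them.

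*That the comparison is tilted in favour of the test product.* The plan describes the opening questions as unprobed, and an open question may bring out complaints as easily as praise. Section 6.1.5 speaks of possible bias towards the company, not towards one product. The test product is derived from the comparator (sections 2.2 and 6.2), and both appear to belong to the sponsor's range. A shift towards the test product is plausible because only that product is discussed, but it is not established.

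*That the whole patient-reported comparison is affected.* The step applies only to volunteers interviewed at V6. Interviews after termination cannot influence forms already completed. With 6-10 interviewees, 25 - 10 = 15 to 25 - 6 = 19 subjects have no interview at all.

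*That the effect could never be examined afterwards.* Interview consent is a form and interviews leave notes (section 6.4.4), so these subjects can be identified and summarised separately. The split is imperfect because interviewees select themselves, but it is available.

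Two further points limit the consequences. TEWL is an instrument measurement, so this route does not reach the primary endpoint. Section 7.1 lists or summarises endpoints that have no stated model. Parts of that section and of the endpoint table are blacked out, so no formal test of these scores can be shown, and there is no success criterion (section 7.5).

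There is also a genuine trade-off: the opening questions come first in order to capture a spontaneous reaction. What stands after all this is the order itself, the absence of a counterpart at V2, and the failure of the CRF argument to cover it.

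**Conclusion.** The point holds in limited form. For subjects whose Interview 1 is part of V6, product questioning by the sponsor precedes the V6 questionnaires and has no equivalent at V2. This is an avoidable asymmetry in an unblinded, fixed-sequence comparison. It risks bias of unknown size, plausibly but not certainly towards the test product.

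On planned numbers, roughly 0-40% of the 25 subjects are exposed, and more only if over ten are interviewed. The consequence is for the interpretation of apparently descriptive patient-reported endpoints, not for the primary analysis. The conclusion assumes that the opening questions are asked in the stated order and that sites do not already collect the forms beforehand. The dilution figures also assume that subjects not interviewed at V6 are unaffected. Correcting this is a worthwhile low-cost improvement, not a condition for the trial's validity.

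**What to change.** In section 6.4.1, under Interview 1, state that the subject completes and hands in all V6 questionnaires, including preference, before any interview question is asked, and that the interviewer is not present while they are filled in. The unprobed questions follow, then the guided ones. The restriction should apply to the interviewer during form completion, not to all sponsor staff throughout the visit. DK001 is a sponsor site (section 6.1.5), and section 6.4.1 (Safety follow-up) allows the sponsor to attend test visits.

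Record for each subject whether Interview 1 was held at V6. V6-V2 changes can then also be summarised separately for those subjects and the rest, with a note that interviewees are self-selected.

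The change needs a short edit to the plan and one recorded item, with no extra visit. Its real cost falls on the interview. The first spontaneous response would come after the leakage scale (10 + 8 + 4 = 22 items), the 23 quality-of-life items and the other forms, and may be coloured by them. That is acceptable because the plan ranks the interviews as supplementary to the CRF data.

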### **Follow-up after the investigation**

Subjects who do not have an ongoing AE, or are not participating in the second interview are not followed up on after termination of the investigation. For ongoing AEs at investigation termination, please see section 14.4. All subjects are encouraged to contact the Investigator or the associated Coloplast nurse after termination of

the investigation, if they experience problems that they believe are related to their participation. This is to ensure that any device-related events are documented and to safeguard the subjects' health.

#### **6.4.2. Activities performed by sponsor representatives**

Sponsor or representative hereof (CRA/Monitor) will make a selection visit, site monitoring visits and site close out visit. At the selection visit Sponsor or representative hereof will ensure that the Investigator is qualified to conduct the investigation, is keen to participate, and has the time, resources and location to run the investigation. When the site has been selected to participate in the investigation, the Sponsor or representative will be responsible for:

- Training of investigator and delegated personnel in the investigation procedures, how to complete the CRF and how to report possible safety issues to Sponsor. All training will be documented by site and sponsor signing the Training Log. However, with any change of staff at site after the initiation, Principle Investigator is responsible for the training of the new staff.
- Identify and contact possible investigation subjects from Coloplast A/S's ostomy user database in Denmark and Sweden by letter, email or advertisement
- Support during the recruitment process
- Support during the test periods
- Monitor site as described in section 6.5 and the Monitoring Plan
- Perform the interviews
- Collect and analyse data
- Equipment for measurements
- Comparator, test products, stoma scissors etc.
- Other equipment used during the visits (gloves, napkins, alcohol-gels etc.)

#### **6.4.3. Foreseeable factors that may compromise the outcome / results**

Use of ostomy accessories may influence the actual performance of the test products. It is not known if accessories will have a "positive" or "negative" influence on the product performance. Subjects are asked not to use adhesive remover during the investigation as adhesive remover residues on the skin can interfere with the objective skin measurements such as TEWL. In addition, subjects who usually use a ring/seal will also be asked not to use these accessories during the investigation. This is to be able to understand the performance of the test products. However, for ethical reasons it is allowed that subjects that experience problems with removing the test products or leakage can use adhesive remover and rings/seals, respectively.

Some subjects enter the study using other accessories to minimise leakage under the baseplate. When this is part of the subject's standard care procedure these subjects may continue to use the accessories, they used when entering the study if they use the same accessories throughout the entire study period. It is important that a subject uses the same kind of accessories when testing the products as this gives the best conditions for comparing the performance of the products.

#### 6.4.4. Flow-chart

Table 4: Chart showing the connection between visits and assessments

[figure not shown]
Endpoint	Source	Performed by	Inclusion visit (V0)	Visit 1 Test visit (V1)	Visit 2 Test visit (V2)	Visit 3 Follow-up/Safety (V3)	Visit 4 Test visit (V4)	Visit 5 Test visit (V5)	Visit 6 Test visit (V6)	Follow-up visit
Oral information		Investigator 	X							
Written informed consent	Informed Consent Form	Subject	X							
Letter of Authority	Letter of Authority	Subject	X							
Consent to interview, including photo/video/tape record and three month contact	Informed Consent Form - Interview	Subject	X							
Declaration of Contraception	Declaration of contraception Form	Subject	X							
Check of inclusion and exclusion criteria	Investigator Binder	Investigator 	X							
Subject number allocated		Investigator	X							
Registration of Baseline data	Investigator Binder	Investigator 	X							
Assessment of subject wellbeing and compliance with CIP	NA	Investigator 	X	X	X	X	X	X	X	X
Collect used products changed at visit	Investigator binder ✓	Investigator 		X	X	X	X	X	X	X
Collect output sample	Investigator binder ✓	Investigator 		X	X					
Arrange dates for the next test visit	NA	Investigator 	X	X	X	X	X	X	X	
Inform Clinical Manager about schedule	[REDACTED]	[REDACTED]	[REDACTED]	[REDACTED]	[REDACTED]	[REDACTED]	[REDACTED]	[REDACTED]	[REDACTED]	[REDACTED]
Comparator product hand-out	Investigator Binder	Investigator 		X						
Subjects trained in how to prepare skin for the comparator product, and how to use, handle, cut and store the product, according to IFU.	Device Accountability Form	Investigator 		X						
Test product hand-out	Device Accountability Form	Investigator 			X	(X)	(X)	(X)		
Subjects training: how to prepare skin for the test product, and how to use, handle, cut and store the product, according to IFU.	Investigator Binder	Investigator 			X					
Hand-out remuneration and obtain signature	Gift card receipt	Investigator  /subject		X	X	X	X	X	X	(X)
Skin assessments and measurements										

Endpoint	Source	Performed by	Inclusion visit (V0)	Visit 1 Test visit (V1)	Visit 2 Test visit (V2)	Visit 3 Follow-up/Safety (V3)	Visit 4 Test visit (V4)	Visit 5 Test visit (V5)	Visit 6 Test visit (V6)	Follow-up visit
OBS!!! For TEWL, hydration and erythema: each measurement should be repeated three times in each spot										
Acclimatisation 30 minutes	Investigator binder ✓	Investigator 		X	X			X	X	X
Picture of peristomal skin (Light box + normal picture)	Investigator binder ✓ SD card	Investigator 		X	X			X	X	X
Picture of reference spot (Light box + normal picture)	Investigator binder ✓ SD card	Investigator 		X	X			X	X	X
Picture of the cut product	Investigator binder ✓ SD card	Investigator 		X	X	X	X	X		
TEWL Inner circle (Four spots)	Investigator Binder	Investigator 		X	X			X	X	X
TEWL Outer circle (Four spots)	Investigator Binder	Investigator 		X	X			X	X	X
TEWL Reference spot	Investigator Binder	Investigator 		X	X			X	X	X
Hydration Inner circle (Four spots)	Investigator Binder	Investigator 		X	X			X	X	X
Hydration Outer circle (Four spots)	Investigator Binder	Investigator 		X	X			X	X	X
Hydration Reference spot	Investigator Binder	Investigator 		X	X			X	X	X
Erythema Inner circle (Four spots)	Investigator Binder	Investigator 		X	X			X	X	X
Erythema Outer circle (Four spots)	Investigator Binder	Investigator 		X	X			X	X	X
Erythema Reference spot	Investigator Binder	Investigator 		X	X			X	X	X
Endpoints completed by subject at visits										
Feeling of security, handling, quality of life, leakage scale questionnaire	Subject questionnaire	Subject			X					X
Skin condition – skin complications	Subject questionnaire	Subject		X	X					X
Skin condition – change of skin complications	Subject questionnaire	Subject			X					X
Stoma condition - questions	Subject questionnaire	Subject		X		X	X	X	X	X
Preference	Subject questionnaire	Subject								X

Endpoint	Source	Performed by	Inclusion visit (V0)	Visit 1 Test visit (V1)	Visit 2 Test visit (V2)	Visit 3 Follow-up/Safety (V3)	Visit 4 Test visit (V4)	Visit 5 Test visit (V5)	Visit 6 Test visit (V6)	Follow-up visit
Endpoints registered by Investigator										
Adverse events incl. supplementary information	Investigator Binder	Investigator 		X	X	X	X	X	X	
Device Deficiencies	Investigator Binder	Investigator 		X	X	X	X	X	X	
Concomitant medication	Investigator Binder	Investigator 	X	X	X	X	X	X	X	
Skin condition – Discoloration/Damage/Raised tissue	Investigator Binder	Investigator 		X	X		X	X	X	
Skin condition – Change in skin complications	Investigator Binder	Investigator 			X				X	
Qualitative data										
Safety interview	Interview notes	Sponsor 				X				
Interview (termination)	Interview notes 	Sponsor 							X	
Interview (follow-up)	Interview notes 	Sponsor 								X

 Qualified site personnel can perform investigation related tasks as investigator representatives. This delegation will be documented in the “Site Personal Signature and Delegation List” for each site. All investigators and investigator representatives will receive oral and written training in all investigation related tasks before they can begin any investigation related tasks. The training will be documented in the Clinical Investigation Training Log.

The interview notes will be stored at the secure Coloplast User Insight Drive.

